5.5 Safety Monitoring Plan

Any adverse safety events occurring in the perioperative period (pre-op, intra-op, or PACU) will be reported by the attending anesthesiologist to the PI and the study coordinator. The PI will record these events and contact the patient to determine the result of these events and arrange any follow-up care that is necessary.

Patients will be instructed to contact the research team to report any adverse events that occur in the postoperative period (after discharge). Patients will be given daytime and evening contact numbers for the PI and the Regional Anesthesia team (on call 24/7) via telephone. These events will be reported to the PI and the study coordinator. The PI will record these events and contact the patient to determine the result of these events and arrange any follow-up care that is necessary.

Serious adverse events will be reviewed by the PI and reported to the IRB promptly within 48 hours. Adverse events of special interest include the following: local anesthetic systemic toxicity, chest pain, shortness of breath, altered sensorium, tinnitus, visual disturbance, and severe dizziness.

6 Statistical Considerations

6.1 Analysis of Primary Objective

6.1.1 The VAS-NRS scale is an 11-point scale that assesses pain from 0- “No pain” to 10- “Worst possible pain”. For this study, a difference of ≥ 2 points will be considered to be clinically significant. Pain scores will be taken measured on departure from the PACU and at each 12-hour interval, and average pain scores for each cohort will be calculated. The area under the curve (AUC) for each cohort will be calculated using the least squares method. The inferiority threshold will be set as ≥ 2 points over 48 hours, which would result in an AUC difference of 96 point-hours.

Prior studies have found an AUC48 for ISB using liposomal bupivacaine to be 136.4 with a standard error of 12.09.¹⁰ There are no data evaluating the AUC48 for ISB using plain bupivacaine with adjuvants; however we estimate that the

Single Injection interscalene brachial plexus nerve block with adjuvants vs. Liposomal bupivacaine interscalene brachial plexus nerve block for total shoulder arthroplasty

pain scores will be within 20% of that of liposomal bupivacaine, resulting in an AUC48 of 163.0 or below, and a similar standard error of 12.09.

With a 2-sample t test using $\alpha = 0.05$ and $\beta = 0.1$, the study will be powered to detect a difference of 96 point-hours between the 2 groups with 36 subjects per arm.

To test for differences in these AUC between the 2 arms, an independent t-test will be used; if the observed p-value is <0.05 , statistical significance will be assumed. Two-sided t-test will be performed for statistical analysis once data collection is complete.

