4.0 Study Outcomes and Study Measures

4.1 Primary Outcome

- 4.1.1 The primary outcome of this study is the area-under-the-curve (AUC) of the mean visual analog scores numerical rating system (VAS-NRS) within the first 48 hours postoperatively. Pain levels (with shoulder movement) will be measured upon arrival to the PACU, at 6 hours, 12 hours, 24 hours, 36 hours, and 48 hours after surgery.
 - 4.1.1.1 The mean AUC48 of the liposomal bupivacaine ISB group was 136.4 with a standard error of 12.09.¹⁰
 - 4.1.1.2 There are no existing data to predict the mean AUC48 for ISB using plain bupivacaine +adjuvants, but we predict that this value will be within 20% of the mean AUC48 of the liposomal bupivacaine group, for a value of ~163.0.

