5.1 Study-Related Activities

Patients will be recruited from 2 sites- Wake Forest Baptist Health (Main Campus) and WFBH Davie. Patient involvement in the study will be initiated upon scheduling of their surgery with the Anesthesiology team. Eligible subjects will be identified via eligibility checklist (Appendix A) and contacted via phone call to inform them of the study and give them a brief overview. On the day of surgery, the consent for the study will be obtained after a pre-operative assessment and prior to initiating the regional block by the RAAPM team.

Single Injection interscalene brachial plexus nerve block with adjuvants vs. Liposomal bupivacaine interscalene brachial plexus nerve block for total shoulder arthroplasty

[figure not shown]
The study coordinator will then assign the patients will receive a study number, and the patient will be randomized by computer software algorithm to one of the study arms:

1. ISB using liposomal bupivacaine
2. ISB using plain bupivacaine with adjuvants

The study will be double blinded to patients, the perioperative nurses, the surgeon, and the study coordinators contacting the patient post-surgery.

To monitor our primary outcomes, patients will be asked to rate their pain level on a visual analog scale (Table 2, Appendix D) upon discharge from the PACU. Following discharge, they will continue to get every 12-hour pain assessments performed by research staff in person and/or over the phone (if they are discharged) until 48 hours have passed.

Table 2: Visual Analog Scale

Additionally, upon discharge, patients will be given a sheet to record the amount of narcotics and the time that they were used (Appendix G). At the 48-hour mark, patient's will be asked to rate their satisfaction with the procedure, and their willingness to recommend it, via Likert scale (Appendix E).

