5.4 Duration of Follow Up

Single Injection interscalene brachial plexus nerve block with adjuvants vs. Liposomal bupivacaine interscalene brachial plexus nerve block for total shoulder arthroplasty

Patients will be followed by research personnel upon arrival to the PACU, again 6 hours postoperatively, and then at 12, 24, 36 and 48 hours after surgery both in the hospital and at home via phone call.

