Appendix C – Pain Assessment Form

Subject Number: _____ DATE: ____/____/____ TIME: ____:____ AM/PM

1 - Rate the intensity of your worst pain in the past 12 hours related to your operated shoulder

0 1 2 3 4 5 6 7 8 9 10

2 - Did you take prescription pain pills in the past 24 hours? YES NO

If yes please circle the medication below

2a1 – Oxycodone (Roxicodone)

2a2 - Hydromorphone (Dilaudid)

2a3 - Hydrocodone + acetaminophen (Vicodin, Norco)

[figure not shown]
2a4- Oxycodone + acetaminophen (Percocet)

2a5 -Diazepam (Valium)

2a6- Alprazolam (Xanax)

Single Injection interscalene brachial plexus nerve block with adjuvants vs. Liposomal bupivacaine interscalene brachial plexus nerve block for total shoulder arthroplasty

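### The primary AUC rule in 6.1 works on cohort averages, names no area method and gives no between-patient standard error; the sections also disagree on score times and score type

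*Combined protocol and SAP*

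**What the plan says.** **Unit and method.** Section 4.1.1 defines the primary outcome as the "area-under-the-curve (AUC) of the mean visual analog scores" over the first 48 hours. Section 6.1 averages the scores within each cohort and continues: "The area under the curve (AUC) for each cohort will be calculated using the least squares method". It then states: "To test for differences in these AUC between the 2 arms, an independent t-test will be used", two-sided, with 36 subjects per arm and an inferiority threshold of 96 point-hours. No section defines an AUC for each patient or names an area rule.

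**Score times.** Section 4.1.1: "Pain levels (with shoulder movement) will be measured upon arrival to the PACU, at 6 hours", then 12, 24, 36 and 48 hours. Section 5.4 agrees: "upon arrival to the PACU, again 6 hours postoperatively, and then at 12, 24, 36 and 48 hours after surgery". Section 6.1 differs: "Pain scores will be taken measured on departure from the PACU and at each 12-hour interval". Section 5.1 starts at PACU discharge, after which "they will continue to get every 12-hour pain assessments performed by research staff". Appendix H, and Table 1 as far as its header is legible, start at PACU departure and keep the 6-hour score.

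**Score type.** Section 4.1.1 specifies pain with shoulder movement. Section 5.1 ties the primary outcome to a rating on the Appendix D scale. Appendix C, which the body text does not cite, asks: "Rate the intensity of your worst pain in the past 12 hours related to your operated shoulder". Appendix H has fields for the worst pain score at 6, 12, 24, 36 and 48 hours.

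**The concern.** The primary result is a difference in AUC judged against 96 point-hours. That judgement needs a standard error that reflects variation between patients. A rule that reduces each arm to one curve and one area does not supply it.

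The curve itself is also not fixed. An analyst would have to decide after data collection how to compute the area, whether the 6-hour score counts, where the curve starts, and what to do with missed or late scores. Score type is more serious in one respect, because it cannot be repaired afterwards. If the forms ask for worst pain over a past interval, pain with movement at set times is not in the data set. The forms as written therefore do not record the outcome that 4.1.1 defines.

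**Working it through.** **1. The plan's own figure.** The threshold reproduces: 2 points × 48 h = 96 point-hours.

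**2. The literal test.** One AUC per cohort gives degrees of freedom 1 + 1 − 2 = 0, so no standard error, p-value or interval exists. One AUC per patient gives 36 + 36 − 2 = 70.

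**3. Does the unit change the estimate?** The trapezoid is a fixed weighted sum of the scores. On 0, 6, 12, 24, 36 and 48 h the weights are 3, 6, 9, 12, 12 and 6. A weighted sum of means equals the mean of weighted sums, so with complete scores on common times the AUC of the mean curve equals the mean of the patient AUCs. A check on 36 simulated patients gave 250.17 both ways. The equality can fail once scores are missed or times differ between patients.

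**4. Schedules side by side.**

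| Section | First score | 6 h score | Later scores |
|---|---|---|---|
| 4.1.1, 5.4 | PACU arrival | yes | 12, 24, 36, 48 h |
| Appendix H; Table 1 as far as legible | PACU departure | yes | 12, 24, 36, 48 h |
| 5.1, 6.1 | PACU discharge or departure | no | every 12 h |

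Without the 6-hour score the trapezoid weights on 0, 12, 24, 36 and 48 h become 6, 12, 12, 12 and 6.

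**5. Size of the open choices.** The documents give no mean profiles, so these are invented. Reference arm: 0, 0, 1, 4, 4, 3.4 at 0, 6, 12, 24, 36, 48 h. Comparators: (i) the same curve × 163.0/136.4, the ratio of the plan's two AUC values; (ii) 0, 0, 2, 5, 4.5, 3.4; (iii) 0, 0, 0, 4, 6, 5.5.

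Reference trapezoid: 9×1 + 12×4 + 12×4 + 6×3.4 = 125.4. Comparator (ii): 9×2 + 12×5 + 12×4.5 + 6×3.4 = 152.4. Difference: 27.0.

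| Arm difference, point-hours | (i) | (ii) | (iii) |
|---|---|---|---|
| Trapezoid, all six scores | 24.5 | 27.0 | 27.6 |
| Without the 6 h score | 25.0 | 30.0 | 24.6 |
| Worst in past 12 h (maximum of the interpolated curve) | 25.2 | 36.0 | 27.0 |
| Last score at 44 h, area not completed to 48 h | 21.7 | 26.7 | 19.3 |
| Area under a least-squares line | 21.9 | 20.1 | 32.9 |
| Area under a least-squares quadratic | 24.9 | 28.8 | 25.0 |
| Area under a least-squares cubic | 25.4 | 28.4 | 27.8 |

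The largest shift from the first row is 36.0 − 27.0 = +9.0, from score type in pair (ii). The 44-hour case reaches 19.3 − 27.6 = −8.3, and the polynomial readings run from −6.9 to +5.3. Reading least squares as a polynomial fit is only one possible reading.

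**The case against.** The strongest reply is that the intent is plain. Section 4.1.1 cites a mean AUC48 with a standard error and speaks of a mean AUC48 for the trial's own plain bupivacaine arm. Section 6.1 assigns that arm a similar standard error and plans a t-test with 36 subjects per arm. Appendix H holds individual scores. A mean AUC with a standard error presupposes patient AUCs, and a competent analyst would compute them. This stands. A reader might infer from the 0 degrees of freedom that the trial cannot deliver a primary result; the documents do not support that. Nor do they support the inference that working on cohort means biases the estimate, given step 3.

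The reply does not close the gap. Section 6.2.2 states the patient-level step for opioid use, converting each patient's total before forming cohort means, while 6.1 has no such step. Nothing in the intent argument supplies an area rule.

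It can also be said that the window is set: 4.1.1 names the first 48 hours and schedules a score at 48 h. That is right. Only the stretch before the first score, an off-schedule last score and missed scores are undefined. Finally, Appendix C is not cited in the body text and 5.1 points to Appendix D. The conflict remains without Appendix C, because the fields in Appendix H are for worst pain.

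**Conclusion.** The point holds as a specification defect in the primary analysis. As written, the test cannot be computed, least squares is not an area rule, the analysis section leaves out a score that is collected, and the forms do not record the defined outcome.

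The size needs care. A reader might conclude that the conflicts in times and score type put the primary conclusion at risk. The figures do not show that: shifts of at most about 9 point-hours against 96, from three invented profile pairs, are examples and not bounds. Nor should the width of the confidence interval at 36 per arm be counted as part of the defect, since it would be the same if 6.1 were perfectly worded.

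The 0 degrees of freedom rest on a literal reading, and the unchanged point estimate rests on complete scores at common times. Correction is worthwhile because it is cheap and removes choices that would otherwise be made after data collection.

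**What to change.** - In 4.1.1 and 6.1, replace the cohort least-squares AUC with an AUC0-48 for each patient by the linear trapezoidal rule on recorded assessment times, including the 6-hour score. Compare patient AUCs between arms and report the mean difference with its 95% confidence interval. Keep cohort mean curves as a figure.
- Reconcile 4.1.1, 5.0, 5.1, 5.4, 6.1 and Appendices C and H to one schedule, stating whether the first score is at PACU arrival or departure, and to one score type asked the same way at every time.
- State how the area is completed before the first score and when the last score is off schedule, and how missed scores are handled.
- Do not try to rescue the Appendix C item by weighting each score by the interval it covers. Twelve-hour recall at 6 h and at 12 h overlaps, and the 6 h recall can reach back before the end of surgery.

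The cost is wording, modest programming and a changed form item if pain with movement is kept, preferably before further scores are collected. No new visits are needed. Adjusting for the preoperative pain score by ANCOVA is an optional precision gain and not part of this defect.

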1.0 Introduction and Background

In 2011, liposomal bupivacaine received FDA approval for the use of local surgical site infiltration, and its use has become common for a variety of abdominal, gynecological, and orthopedic surgeries, with varying efficacy.^{1,2,3} Studies evaluating the efficacy of liposomal bupivacaine for regional procedures have also displayed mixed results.⁴

Liposomal bupivacaine has recently been approved by the FDA for use in brachial plexus blocks for patients undergoing major shoulder surgery.⁵ Per the manufacturer's data, ISB using liposomal bupivacaine provided significant pain reduction in the first 48 hours after surgery compared to ISB using placebo, establishing that liposomal bupivacaine has an opioid sparing effect in this patient population without significant risk.

A recent study compared the addition of liposomal bupivacaine to plain bupivacaine for interscalene blocks in patients undergoing shoulder surgery, and found a modest improvement in pain.⁶

At a cost of about \$300 per administration for liposomal bupivacaine, there are significant economic impacts to be considered, given that plain bupivacaine is significantly less expensive. Data from future studies are required to perform a cost-benefit analysis for this new drug.

Common and relatively inexpensive adjuvants have been shown to extend the duration of analgesia provided by interscalene nerve blocks (ISB) using plain bupivacaine, with a significant analgesic effect extending up to 48 hours postoperatively.⁷⁻⁹

To date, there has been no study comparing the efficacy of ISB using liposomal bupivacaine vs plain bupivacaine with these common adjuvants, such as epinephrine, dexamethasone, clonidine, and buprenorphine.

The purpose of this study is to determine whether the use of plain bupivacaine with common adjuvants for ISB provides non-inferior analgesic results compared to the use of liposomal bupivacaine for ISB, in patients undergoing primary total shoulder arthroplasty.

LB= Liposomal bupivacaine

PBA= Plain bupivacaine + adjuvants

ISB= Interscalene peripheral nerve block

Single Injection interscalene brachial plexus nerve block with adjuvants vs. Liposomal bupivacaine
interscalene brachial plexus nerve block for total shoulder arthroplasty

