4.2 Secondary Outcomes

- 4.2.1 Mean VAS-NRS pain score at 48 hours.
 - 4.2.1.1 For patients undergoing ISB with liposomal bupivacaine, the mean VAS pain score at 48 hours was 3.39 with a standard error of 0.37.¹⁰
 - 4.2.1.2 There are no existing data to predict the mean VAS pain score at 48 hours for patients undergoing ISB with plain bupivacaine + adjuvants, however a similar study using plain bupivacaine alone demonstrated a mean NRS (similar to VAS) pain score of 5.5 with standard error +/-0.5⁶. We expect the mean pain score to be slightly below this value, approximately 4.5.
- 4.2.2 Postoperative opioid consumption
 - 4.2.2.1 The mean rescue opioid consumption (in IV morphine equivalents) in the first 48 hours after receiving ISB using liposomal bupivacaine was 12.0 +/- 2.3 in a previous study.¹⁰
 - 4.2.2.2 We expect the patients treated with plain bupivacaine and adjuvants to use a similar average of 12.0 intravenous morphine equivalents in the first 48-hours following surgery. For the purpose of this study, we will convert IV morphine equivalents to oral codeine equivalents.
- 4.2.3 Satisfaction with surgical experience
 - 4.2.3.1 At the 48 hour mark, the patient's satisfaction with the surgical experience, satisfaction with pain control, and willingness to recommend the procedure to another patient will be assessed via Likert scale. Adverse events will also be evaluated.

Single Injection interscalene brachial plexus nerve block with adjuvants vs. Liposomal bupivacaine interscalene brachial plexus nerve block for total shoulder arthroplasty

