6.2 Analysis of Secondary Objectives

- 6.2.1 For the mean VAS-NRS score at 48 hours, prior studies have found an average score of 3.8 with a standard deviation of 2.88 (standard error of 0.36) for ISB using liposomal bupivacaine.¹⁰ There have been no studies to evaluate the pain scores after ISB using plain bupivacaine with adjuvants. This study will be powered to detect a difference of at least 0.4 on the VAS-NRS scale. We will define the threshold for inferiority as a difference of ≥ 2 points on the VAS scale. Analysis will be conducted using a two-sample t test with $\alpha = 0.05$ and $\beta = 0.1$.
- 6.2.2 For the comparison of post-operative opioid consumption, each patient's total post-operative opioid usage during the first 48 hours will be converted to oxycodone equivalents. The geometric mean opioid consumption for each cohort will be calculated, and the two cohorts will be compared for statistical difference using a two-sample t test, with $\alpha = 0.05$ and $\beta = 0.1$.
- 6.2.3 Patient satisfaction will be assessed on POD#2 by 5-point Likert rating scale, and via a binary question of "would you recommend this pain relief regimen to the next patient". The results of these questions will be compared with a Fisher's Exact Test, with $\alpha = 0.05$.

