6.3 Power and Sample Size

We will have a power of 80%, as described in 10.1.1, with a sample size of 36 patients in each arm for a total of 72 patients, plus 8 patients to allow for attrition, for a total of 80 patients.

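### The trial asks a non-inferiority question, but the primary analysis is a two-sided test for any difference, and no rule compares the result with the 96 point-hour threshold

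*Combined protocol and SAP*

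**What the plan says.** Section 1.0 gives the purpose as to "determine whether the use of plain bupivacaine with common adjuvants for ISB provides non-inferior analgesic results compared to the use of liposomal bupivacaine". Section 2.1.1 hypothesises similar pain relief in the two arms. No section states a superiority aim.

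Section 6.1.1 sets a threshold: "The inferiority threshold will be set as ≥ 2 points over 48 hours", which it converts to 96 point-hours (2 × 48). It then says that "the study will be powered to detect a difference of 96 point-hours between the 2 groups with 36 subjects per arm", at α = 0.05 and β = 0.1. The analysis is: "To test for differences in these AUC between the 2 arms, an independent t-test will be used". Significance is declared at p < 0.05, and the test is two-sided.

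Section 6.2.1 follows the same pattern for the 48-hour pain score: "We will define the threshold for inferiority as a difference of ≥ 2 points on the VAS scale", followed by an ordinary two-sample t-test that does not use the 2 points.

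No section gives a confidence interval, a null hypothesis placed at the threshold, or a rule for concluding non-inferiority.

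**The concern.** A t-test against zero asks whether the arms differ at all. The stated question is whether plain bupivacaine with adjuvants is worse by as much as 96 point-hours. The answers can diverge in two ways. A non-significant result may leave a loss of 96 or more inside the confidence interval. A significant result may come with an interval that lies wholly below 96, so that non-inferiority is in fact shown.

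The result hoped for here is a non-significant p-value, and the plan does not say what one would mean. If it were read as support for the hypothesis of similarity, a small or noisy trial would be more likely to succeed than a precise one. If the rule is chosen after the data are seen, either outcome could be presented as success.

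**Working it through.** **Inputs**
- Margin 96 point-hours, 36 per arm, two-sided α = 0.05, β = 0.1 (6.1.1). Section 6.3 gives the power as 80% instead.
- Liposomal bupivacaine AUC48 136.4, SE 12.09; comparator predicted at 163.0 or below (4.1.1, 6.1.1). The largest predicted difference is 163.0 − 136.4 = 26.6.
- 48-hour score: mean 3.8, SD 2.88, SE 0.36 (6.2.1), but mean 3.39, SE 0.37 in 4.2.1.1. Comparator: "We expect the mean pain score to be slightly below this value, approximately 4.5" (4.2.1.2).
- The AUC48 SD is not stated, so three values are used:
  - 97: 12.09 × √64 = 96.7, assuming the prior arm had n = (2.88/0.36)² = 64.
  - 124 and 143: the SDs at which 36 per arm gives 90% or 80% power for a difference of 96 in a two-sided 0.05 t-test.

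**The plan's own 36 per arm.** As worded (two-sided 0.05, 90% power, difference 96), SD 97 needs 23 per arm. SD 2.88 × 48 = 138.24 needs 44 (normal approximation). The stated 36 appears with one-sided 0.05, a 2-point difference and SD 2.88: 2 × (1.645 + 1.282)² × (2.88/2)² = 35.5, rounded up to 36. That is not the two-sided test the plan specifies.

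**The two rules.** Let d be the observed difference (plain with adjuvants minus liposomal) and h = 1.994 × SD × √(2/36) the 95% half-width (70 df). The planned test is significant if |d| > h. A margin rule concludes non-inferiority if d + h < 96.
- If h < 48, any d between h and 96 − h is significantly worse yet non-inferior.
- If h > 48, any d between 96 − h and h is non-significant yet does not exclude 96.
- The switch is at an observed SD of 48/(1.994 × √(2/36)) = 102.

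Examples: at SD 97, h = 45.5, and d = 48 gives p = 0.039 with interval 2.5 to 93.5. At SD 143, h = 67.4, and d = 50 gives p = 0.14 with interval −17.4 to 117.4.

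**How often, for AUC48** (36 per arm, 4 million simulated trials, SD estimated in each)

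| | SD 97 | SD 124 | SD 143 |
|---|---|---|---|
| True difference 26.6: non-significant, 96 not excluded | 1.3% | 21% | 36% |
| True difference 26.6: significantly worse, yet non-inferior | 7.3% | 0.1% | 0.0% |
| True difference 13.3: non-significant, 96 not excluded | 0.6% | 14% | 27% |
| True difference 0: non-significant, 96 not excluded | 0.2% | 7.5% | 17.5% |
| True loss 96: non-significant | 1.4% | 10% | 20% |

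Under the margin rule with a 95% interval, the last row would be replaced by 2.5% false non-inferiority at every SD.

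**48-hour score.** h = 1.994 × 2.88 × √(2/36) = 1.35 points. An observed difference of 4.5 − 3.8 = 0.7 gives p = 0.31 and interval −0.65 to 2.05: non-significant, with 2 points not excluded. If the true difference is 0.7, 36% of trials end that way; if it is 4.5 − 3.39 = 1.11, 38% do. At a true 2-point loss, 17% are non-significant. With SE 0.37 (SD 0.37 × 8 = 2.96) these become 38%, 41% and 19%.

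**The case against.** The strongest reply is that a study powered to detect 96 makes non-significance informative. At SD 97, the only value tied to the cited prior data, this is largely true. A true loss of 96 would be non-significant in 1.4% of trials, fewer than the 2.5% the margin rule would wrongly pass, and the t-test errs mainly in the conservative direction. That stands for AUC48 at that SD. But the SD of 97 rests on an inferred n, and at an SD that matches the plan's own power claims the reassurance is gone.

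Four further points are fair:
- The SDs of 124 and 143 are solved backwards on the premise that 36 was derived for a two-sided test, and the figure may have come from a one-sided calculation.
- The 26.6 is the plan's ceiling, not its expectation, so the table also shows 13.3 and 0.
- The error rates at a true loss matter only if non-significance is read as non-inferiority, which the plan does not say; nor does 6.2.1 say that its t-test is two-sided.
- The plan does define what counts as inferior. What it lacks is the comparison of the estimate and its uncertainty with that threshold.

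None of this supplies a decision rule, and the mismatch does not depend on the SD.

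**Conclusion.** The concern holds and must be fixed. The mismatch between question and test follows from the text of Sections 1, 6.1.1 and 6.2.1 and needs no assumption. Its practical size does. For AUC48 it runs from small (SD 97, n of 64 assumed) to substantial (SD 124 or 143, back-solved from the stated power). For the 48-hour score, where the plan gives the SD, it is substantial: about a third of trials would be non-significant without excluding 2 points, at the differences the plan itself predicts.

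**What to change.** In 6.1.1:
- Compute AUC48 for each patient. The text now reads "The area under the curve (AUC) for each cohort will be calculated using the least squares method", although a t-test already presupposes one value per patient.
- Report the mean difference (plain bupivacaine with adjuvants minus liposomal bupivacaine) with its two-sided 95% confidence interval, and conclude non-inferiority only if the upper limit is below +96 point-hours. The 95% level matches the plan's two-sided α of 0.05; if another level is intended, state it.
- State that a non-significant difference test is not evidence of similarity.
- Restate the power for the non-inferiority rule, with the assumed SD and true difference, and reconcile the 90% in 6.1.1 with the 80% in 6.3.

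In 6.2.1, apply the same interval rule to the 2-point threshold.

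The rule needs no new data. The cost lies in what the restated power may show for AUC48:

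| | SD 97 | SD 124 | SD 143 |
|---|---|---|---|
| Power, 36 per arm, true difference 0 | 99% | 90% | 80% |
| Power, 36 per arm, true difference 26.6 | 85% | 65% | 53% |
| Per arm for 80% power at 26.6 | 32 | 52 | 68 |

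With the plan's attrition allowance (72/80 = 0.9), 52 per arm means 104/0.9, or 116 enrolled, and 68 means 136/0.9, or 152, against the planned 80. At one-sided 0.05, if that is what the sponsor intends, power at 26.6 with 36 per arm is 91%, 76% or 65%, and 80% power needs 25, 41 or 54 per arm. The level should be fixed and justified before outcome data are seen.

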5.0 Treatment Plan

Table 1- Protocol stages

| | Day of Surgery- Pre-op | Intraoperative | 15 departure from PACU | 6 hours postop | 12 hours postop | 24 hours postop | 36 hours postop | 48 hours postop |
|------------------------------------------------------------------------------------|---------------------------|----------------|---------------------------------|----------------------|-----------------------|-----------------------|-----------------------|-----------------------|
| Pre-operative pain score | X | | | | | | | |
| Preoperative multimodal regimen unless contraindicated | X | | | | | | | |
| Receive ISB with Exparel or plain bupivacaine + adjuvants | X | | | | | | | |
| Receive short-acting IV opioids if needed | | X | | | | | | |
| Rescue opioids if needed | | | X | X | X | X | X | X |
| Postoperative multimodal regimen | | | | X | X | X | X | X |
| Pain score assessment in diary | | | X | X | X | X | X | X |
| Patent diary of narcotic use | | | X | X | X | X | X | X |
| Study coordinator contact via phone call | | | | | | X | | X |
| Patient satisfaction assessed via Likert scale. Review of potential adverse events | | | | | | | | X |

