Appendix H- Data Collection Form

| | |
|--------------|-----------------------------------------|
| | Assigned Study Number: |
| | WakeOne MRN |
| Demographics | Age |
| | Sex |
| Procedure | Comorbidities |
| | Pre-surgical analgesics |
| Medical Hx | Preop pain score |
| | Pre-op multimodal analgesics |
| | Post-Block assessment |
| Pre-Op | Intra-op Narcotics (PO oxy equivalents) |
| | Pain score in PACU p/t discharge |
| Intraop | PACU block assessment |
| | PACU opioids (PO oxy equivalents) |
| | +6hr worst pain score (VAS) |
| PACU | |
| | |

Single Injection interscalene brachial plexus nerve block with adjuvants vs. Liposomal bupivacaine interscalene brachial plexus nerve block for total shoulder arthroplasty

| | |
|------------------|-----------------------------------------------------------------------------------------------------------------------------------------------------------------------------------------------------------------------------------------------------------------------------------------------------------------------------------------------------------------------------------------------------------------------------------------------------------------------------------------------------------------|
| | 
+12h worst pain score (VAS)
 
+24h worst pain score (VAS)
 
+36h worst pain score (VAS)
 
+48h worst pain score (VAS)
 
+6hr opioid use (PO oxy eq)
 
+12h opioid use (PO oxy eq)
 
+24h opioid use (PO oxy eq)
 
+36h opioid use (PO oxy eq)
 
+48h opioid use (PO oxy eq)
 
Likert Satisfaction #1
 
Likert satisfaction #2 Nonopiod Analgesics Used Side effect evaluation (Itching, Nausea/vomiting)
 |
| Post OP | |
| Off study | 
("OFF" if applicable)
 
Reasons:
 |

Date of study completion:

Evaluable subject?

Protocol deviations?

Single Injection interscalene brachial plexus nerve block with adjuvants vs. Liposomal bupivacaine interscalene brachial plexus nerve block for total shoulder arthroplasty

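### The primary AUC48 comparison is an unadjusted t-test, although a pre-operative pain score is collected that could be pre-specified as a covariate at almost no cost

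*Combined protocol and SAP*

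**What the plan says.** Section 6.1 names the primary test: "To test for differences in these AUC between the 2 arms, an independent t-test will be used". It adds: "Two-sided t-test will be performed for statistical analysis once data collection is complete". No covariate, regression model or stratified analysis is named for this or any other outcome.

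A baseline value is nevertheless collected. Table 1 (section 5.0) has a row "Pre-operative pain score", marked for the pre-operative column on the day of surgery. The data collection form in Appendix H has the field "Preop pain score". Neither section 6.1 nor section 6.2 refers to it.

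Section 1.0 frames the study as non-inferiority of plain bupivacaine with adjuvants (PBA) to liposomal bupivacaine (LB). Section 6.1 sets the inferiority threshold at 2 points over 48 hours, "which would result in an AUC difference of 96 point-hours".

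**The concern.** If pre-operative pain predicts postoperative pain, a t-test leaves the predictable part of the variation in the error term. A chance difference between arms in baseline pain is also left uncorrected, and section 5.1 describes no stratified randomisation that would limit it.

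For a non-inferiority question the stake is the width of the interval for the PBA minus LB difference, because its upper limit has to fall below 96 point-hours. A covariate that is already on the form could narrow that interval without a further patient or measurement.

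**Working it through.** **Inputs**

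- Patients: 36 per arm, N = 72 (sections 6.1 and 6.3).
- Threshold: 96 point-hours (section 6.1).
- Predicted difference: 20% of the LB mean of 136.4, so 0.20 × 136.4 = 27.28 point-hours. The plan rounds the PBA mean to 163.0, which gives 26.6.
- SD of AUC48: not stated. Section 6.1 gives only a standard error of 12.09, without its n. Section 6.2.1 gives SD 2.88 and SE 0.36 for the 48-hour score from the same source, so n = (2.88/0.36)² = 64. If the same n lies behind the AUC48 figure, SD = 12.09 × 8 = 96.7. This is an assumption.
- Correlation r of pre-operative pain with AUC48: not given. The range 0.1 to 0.5 is assumed.

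**The plan's own figure**

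Detecting 96 point-hours at two-sided 0.05 and 90% power needs n = 2 × [(1.960 + 1.282) × 96.72/96]² = 21.3, so 22 per arm (23 by noncentral t). The stated 36 is not reproduced with this SD. It would need an SD of about 126, or about 145 at 80% power. Section 6.3 does state the lower power ("We will have a power of 80%, as described in 10.1.1"), whereas section 6.1 sets β at 0.1. These are separate matters. What counts here is that power to detect a full 96 at 36 per arm is already 98.6% with this SD, so adjustment has little to add to that target. Its value lies in the non-inferiority interval.

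**Effect of adjustment**

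- Unadjusted: SE = 96.72 × √(2/36) = 22.80. Half-width = t(0.975, 70) × SE = 1.994 × 22.80 = 45.5.
- ANCOVA with one covariate: the variance is multiplied by (1 − r²) × (N − 3)/(N − 4) = (1 − r²) × 69/68, with 69 degrees of freedom. The factor 69/68 is the cost of estimating the covariate slope.
- Non-inferiority power: noncentral t at one-sided 0.025, with noncentrality (96 − 27.28)/SE = 68.72/SE.
- Equivalent n per arm = 36/variance factor.

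| Analysis | Variance factor | 95% half-width (point-hours) | Non-inferiority power | Equivalent n per arm |
|---|---|---|---|---|
| Unadjusted t-test | 1.000 | 45.5 | 84.4% | 36 |
| ANCOVA, r = 0.1 | 1.005 | 45.6 | 84.3% | 35.8 |
| ANCOVA, r = 0.2 | 0.974 | 44.9 | 85.3% | 37.0 |
| ANCOVA, r = 0.3 | 0.923 | 43.7 | 87.1% | 39.0 |
| ANCOVA, r = 0.4 | 0.852 | 42.0 | 89.6% | 42.2 |
| ANCOVA, r = 0.5 | 0.761 | 39.7 | 92.6% | 47.3 |

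Break-even is where (1 − r²) × 69/68 = 1, so r = √(1/69) = 0.12.

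**Chance imbalance**

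The between-arm difference in mean baseline has a standard error of √(2/36) = 0.236 baseline SDs. An imbalance of 1.96 standard errors moves the unadjusted AUC48 difference by 1.96 × 0.236 × r × 96.7. That is about 13 point-hours at r = 0.3 and 22 at r = 0.5. ANCOVA corrects for such a shift in the trial at hand.

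**The case against.** The strongest reply is that nothing here is wrong. Section 5.1 randomises patients, and under randomisation the t-test is valid. That stands.

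A reader might infer that the t-test is biased by baseline imbalance and that ANCOVA removes the bias. The design does not support this. Over repeated randomisations the unadjusted difference is unbiased, and the t-test's standard error already carries the variation that chance imbalance adds. Adjustment reduces variance and corrects the imbalance that happens to occur; there is no systematic bias to remove.

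A reader might also infer that precision is certainly being thrown away. The documents give no correlation, and some features could keep it modest:

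- Exclusions 3.2.4 and 3.2.7 remove chronic pain, higher opioid use and other painful conditions, which may narrow the baseline range.
- The outcome is measured after a nerve block and with rescue opioids available.
- Section 4.1.1 measures pain on shoulder movement, while the plan does not say whether the pre-operative score is at rest or on movement.

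At r = 0.1 the gain is nil, and at r = 0.2 it is 0.6 point-hours of half-width. This objection limits the size of the claim. It does not argue for leaving the score unused, because the loss when r is near zero is negligible.

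Third, the plan as written has no confidence interval to narrow. Section 6.1 decides by a two-sided difference test at p < 0.05. This also stands: the benefit against 96 point-hours arises only once the interval is the stated basis for the non-inferiority conclusion.

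Finally, the SD is inferred, and section 4.2.1.1 gives a different mean and standard error (3.39 and 0.37) for the 48-hour score from the same source. Pairing 0.37 with SD 2.88 gives an AUC48 SD of 12.09 × 2.88/0.37 = 94.1, which changes little.

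**Conclusion.** The point holds as a recommended improvement. The primary analysis ignores a baseline score that the plan schedules and records, and pre-specifying adjustment for it is close to free.

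On the stated assumptions (SD 96.7, 36 per arm, true difference 27.28, one covariate), non-inferiority power moves from 84.4% to between 84.3% at r = 0.1 and 92.6% at r = 0.5. It comes close to the 90% implied by section 6.1's β only near r = 0.4 (89.6%). The omission itself is certain from the text. The size of the benefit is not, because it rests on an assumed correlation and an inferred SD. The documents support neither a claim of bias nor a claim that any particular amount of precision is lost.

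**What to change.** Amend section 6.1 before unblinding, since a covariate chosen afterwards is open to challenge:

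- Define AUC48 for each patient. Section 6.1 now describes it by cohort, and ANCOVA needs individual values.
- Make the primary analysis a linear model of AUC48 on arm and pre-operative pain score. Site may be added, since section 5.1 names two, but its benefit cannot be quantified from the documents. If it explains nothing, it costs a further degree of freedom (at r = 0.2, half-width 45.2 and power 84.8% with site, against 44.9 and 85.3% without).
- Report the adjusted PBA minus LB difference with its 95% CI, and base the non-inferiority conclusion on that interval against 96 point-hours.
- Keep the unadjusted t-test as a sensitivity analysis.
- State how a missing pre-operative score is handled, and whether the score is taken at rest or on movement.

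The cost is SAP wording and about one degree of freedom. No new patients or measurements are needed.
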